1 INTRODUCTION

1.1 LIGHT CHAIN (AL) AMYLOIDOSIS

Systemic amyloidoses are a complex group of diseases caused by tissue deposition of misfolded proteins that result in progressive organ damage. The most common type, light chain (AL) amyloidosis or primary systemic amyloidosis, involves a hematologic disorder caused by clonal plasma cells that produce misfolded immunoglobulin light chains. Overproduction of misfolded light chains by plasma cells results in both soluble, aggregated forms of light chains and insoluble, fibrillar deposits of abnormal AL protein (amyloid), in the tissues and organs of individuals with AL amyloidosis. Clinical features of AL amyloidosis include a constellation of symptoms and organ dysfunction including cardiac, renal, and hepatic dysfunction, gastrointestinal involvement, neuropathy and macroglossia. The mechanisms by which amyloidogenic immunoglobulin light chains result in organ dysfunction are not well characterized; however, it is hypothesized that both amyloid deposits and prefibrillar aggregates may contribute to cytotoxic effects on organs observed in patients with AL amyloidosis.

AL amyloidosis is a rare disorder. Although the exact incidence of AL amyloidosis in the United States (US) is unknown, a weighted average from 5 sources ([Kyle et al, 1992](#); [Simms et al, 1994](#); [Kyle et al, 2002](#); [Kyle et al, 2006](#); [Junicon Study](#)) estimates the incidence to be 7.6 new cases per million population per year, which is approximately 2300 new cases per year.

Approximately, two thirds of AL amyloidosis patients present with one or two major organ systems involved (e.g., cardiac, renal, gastrointestinal tract, hepatic, autonomic nervous system, peripheral nervous system, soft tissues) while a third of patients present with more than two systems involved ([Kyle et al, 1992](#)). AL amyloidosis is most commonly associated with cardiac and/or renal dysfunction, with overt restrictive cardiomyopathy observed in approximately 50% of all cases, and subclinical cardiac involvement detected in almost every case at autopsy or on endomyocardial biopsy ([Falk and Dubrey, 2010](#)).

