3.2 STUDY ENDPOINTS

3.2.1 Primary

- Assessment of the safety and tolerability of NEOD001 as assessed by vital signs, duration of therapy, 12-lead electrocardiograms (ECGs), routine laboratory assessments, and frequency and severity of AEs

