4.2 EXCLUSION CRITERIA

Subject must *not* meet any of the following:

1. Any new medical contraindication or clinically significant abnormality on physical, neurological, laboratory, vital signs, or ECG examination (e.g., atrial fibrillation; *with the exception* of subjects for whom the ventricular rate is controlled) that precludes continued or initiation of treatment with NEOD001 or participation in the study
2. History of Grade ≥ 3 infusion-associated adverse events (AEs) or hypersensitivities to NEOD001 or any of its excipients

3. Treatment with any anticancer therapy (standard or investigational) within the 14 days prior to the first dose of study drug. In addition, subjects must have fully recovered (i.e., National Cancer Institute Common Terminology Criteria for Adverse Events [CTCAE] Grade 1 [*exception*: subjects with prior bortezomib may have CTCAE Grade 2 neuropathy]) from the clinically significant toxic effects of that treatment
4. Received any of the following within the specified time frame prior to the first administration of study drug:
 - Hematopoietic growth factors, transfusions of blood or blood products within 1 week
 - Major surgery within 2 weeks
 - Radiotherapy within 2 weeks
 - Transplant within 8 weeks
 - Investigational drug other than NEOD001 within 4 weeks
 - Another experimental anti-amyloid therapy other than NEOD001 within 2 years
5. Uncontrolled symptomatic orthostatic hypotension
6. Myocardial infarction, uncontrolled angina, uncontrolled ventricular arrhythmias, or electrocardiographic evidence of acute ischemia, within 6 months prior to the first dose of study drug
7. Uncontrolled infection
8. Secondary malignancy, *with the exception of*:
 - Adequately treated basal cell carcinoma, squamous cell carcinoma, or in situ cervical cancer
 - Adequately treated stage I cancer from which the subject is currently in remission
 - Any other cancer from which the subject has been disease-free for ≥ 3 years
9. Uncontrolled human immunodeficiency virus (HIV), hepatitis B, or hepatitis C infection
10. Women who are lactating

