2.3. Study Endpoints

2.3.1. Primary Endpoints

The primary study endpoints are the frequency and severity of AEs, changes in laboratory assessments from OLE baseline, and change in vital signs and 12-lead ECGs from NEOD001 baseline and OLE baseline.

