9.6. Electrocardiograms

ECGs measurements will be made in triplicate, 5 to 10 minutes apart and assessed by a central reader. For summary purposes, the mean of the three measurements will be used. ECG parameters including, time between 2 consecutive R waves [RR], PR interval, QRS duration, QT (uncorrected) interval, QT interval corrected by the Bazett's formula [QTcB], and QT interval corrected by the Fridericia's formula [QTcF], will be summarized using descriptive statistics will be presented for observed values, change from NEOD001 baseline, change from OLE baseline, at each NEOD001 post-baseline time point, and at each OLE post-baseline time point.

A categorical summary of the following abnormal maximum mean triplicate QTcF values will be presented: >450 msec, >480 msec, and >500 msec. Change from NEOD001 baseline and OLE baseline summaries will also be presented for measurements that represent a change from baseline >30 msec and >60 msec. Three separate listings for those subjects with any QTcF >450 msec or a QTcF change from either baseline >30 msec, any QTcF >480 msec or a QTcF change from either baseline >30 msec, and any QTcF >500 msec or a QTcF change from baseline >60 msec will be presented. The observation(s) meeting criteria for inclusion will be flagged in the listing.

Overall interpretation results for ECGs and the investigator interpretation results are collected as normal, abnormal not clinically significant, and abnormal clinically significant. Subjects whose interpretation shifts from normal to abnormal clinically significant or not clinically significant will be listed separately including description of the abnormality and any associated comments.

All ECG results will be presented in by-subject data listings.

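### The ECG interpretation-shift listing in SAP 9.6 takes only subjects who start at normal, so worsening from abnormal not clinically significant to abnormal clinically significant is not selected

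*SAP*

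**What the plan says.** Both documents place the 12-lead ECG in the primary endpoint. Protocol 3.2.1 includes it among the safety measures ("duration of therapy, 12-lead electrocardiograms (ECGs), routine laboratory assessments, and frequency and severity of AEs"). SAP 2.3.1 words it as "change in vital signs and 12-lead ECGs from NEOD001 baseline and OLE baseline".

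SAP 9.6 says that the overall and investigator interpretations "are collected as normal, abnormal not clinically significant, and abnormal clinically significant". It then gives the rule for the one output aimed at a change of interpretation: "Subjects whose interpretation shifts from normal to abnormal clinically significant or not clinically significant will be listed separately", with a description of the abnormality and any comments.

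The section also plans:

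- descriptive statistics for RR, PR, QRS, QT, QTcB and QTcF, with change from both baselines;
- a categorical summary of QTcF values and changes;
- three QTcF listings, for which "The observation(s) meeting criteria for inclusion will be flagged in the listing";
- a general listing: "All ECG results will be presented in by-subject data listings".

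No shift table is planned for the interpretation, and no listing is planned for a move from NCS to CS.

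**The concern.** A listing of this kind exists to bring forward the subjects whose ECG reading got worse. As written, it brings forward a subject who moves from normal to an abnormality judged not clinically significant. It passes over a subject whose existing abnormality becomes clinically significant, which on the SAP's own scale is the more important move.

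The disease makes an abnormal starting ECG plausible. Protocol 1.1 describes "overt restrictive cardiomyopathy observed in approximately 50% of all cases, and subclinical cardiac involvement detected in almost every case". Exclusion criterion 1 in Protocol 4.2 bars clinically significant ECG abnormalities that preclude treatment or participation, but makes an exception within its atrial fibrillation example for "subjects for whom the ventricular rate is controlled". Subjects may therefore enter with an abnormal tracing that the investigator does not regard as a bar to treatment.

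At stake is how the output is read. A short list of subjects with ECG worsening could be taken as cardiac reassurance when one class of clinically significant worsening was never eligible for it.

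**Working it through.** The plan gives no figure to reproduce. The check is a count of transitions, followed by a comparison of the planned outputs.

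**1. Inputs.** Three ordered levels (SAP 9.6): normal < NCS < CS. Selection rule (SAP 9.6): the start must be normal, and the end is NCS or CS.

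**2. Worsening moves.** Three ordered levels give 3 × 2 / 2 = 3 possible worsening moves.

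| Move | Selected by the SAP 9.6 shift listing? |
|---|---|
| normal to NCS | yes |
| normal to CS | yes |
| NCS to CS | no |

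The rule covers 2 of 3. Of the two moves that end at CS, it covers one.

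**3. Where else an NCS-to-CS subject would appear.**

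- *General ECG listing (SAP 9.6).* The subject is present, but the section specifies no flag for an interpretation shift. The flag it does specify belongs to the QTcF listings.
- *QTcF listings (SAP 9.6).* The subject is selected whatever the starting interpretation, but only if a QTcF threshold or change criterion is met. A new conduction block, arrhythmia or ischemic change need not meet one.
- *RR, PR and QRS summaries (SAP 9.6).* The subject contributes to group statistics that bear on rate and conduction. These do not identify individuals.
- *Adverse events.* Protocol 7.1 gives new clinically significant abnormalities in physiological testing as an example of an AE, so a reporting route exists. It depends on the investigator. Protocol 7.4.3 adds that progression, including progression of organ dysfunction, should not be reported as a specific AE or SAE, although a serious event arising from it is reported under its sign or symptom.

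The listing is therefore the only planned subject-level output that selects on interpretation shift. It is not the only place where a worsening ECG could be seen.

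**4. Comparison within the SAP.** For laboratory tests the SAP tabulates shifts from every starting level: CTCAE grade shifts in SAP 9.3.2, and a 3-by-3 low/normal/high table in SAP 9.3.3 for tests that cannot be graded. ECG interpretation is also a three-level scale but has a rule limited to normal starters. No reason is given.

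**5. What the rule leaves open.** SAP 9.6 does not say which baseline or visit the shift is measured from, although SAP 2.2.4 defines two baselines. It also does not say whether the overall or the investigator interpretation decides.

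**6. Number of subjects.** This would need the share of subjects who are NCS at OLE baseline and the share of those who later reach CS. Neither document gives either share, so no count is computed.

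**The case against.** The strongest case on the other side is that little is hidden. Every ECG result is listed by subject, so any shift can be recovered. The QTcF listings ignore the starting interpretation. RR, PR and QRS changes are summarised for everyone, and these summaries address the primary endpoint as SAP 2.3.1 words it. A new clinically significant finding should also reach the AE tables. The study is an uncontrolled extension with no inferential safety comparison (SAP 9), in a discontinued program (SAP 11). All of this stands, and it holds the severity down. It does not explain why the milder move is selected and the NCS-to-CS move is not.

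A reader might infer three stronger things that the documents do not support.

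- *That subjects who are abnormal at baseline can never be flagged, however much their ECG worsens.* The QTcF listings and AE reporting contradict this. Because the reference point is not named, such a subject could even enter the shift listing after an intervening normal reading, if the rule were applied visit to visit.
- *That about half of the roughly 70 subjects are affected.* The 50% in Protocol 1.1 is a rate of cardiomyopathy in the disease, not of NCS readings at OLE baseline. Seventy is an upper limit: SAP 2.2.1 says up to approximately that number, the parent study enrolled 69 (Protocol 1.3.2), and entry needs at least 9 months of treatment there. Even a correct count of NCS starters would not be a count of moves from NCS to CS.
- *That rate-controlled atrial fibrillation proves the point.* Such a tracing could be coded CS at baseline. No rule based on a worse category would then select that subject.

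**Conclusion.** The gap is real and minor. Followed exactly, SAP 9.6 selects two of the three worsening moves and omits NCS to CS, so its only subject-level interpretation-shift output is incomplete for a measure that belongs to the primary endpoint. The affected subjects stay in the by-subject ECG listings and may surface through AEs or QTcF criteria.

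The conclusion rests on the plain reading that a listed subject must start at normal. That some subjects start at NCS is an inference from the disease description and the entry criteria. It is plausible but not quantified, and the number who would move to CS could be small.

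**What to change.** Reword the rule in SAP 9.6 so that it lists every subject whose post-baseline interpretation is worse than at OLE baseline: normal to NCS, normal to CS, and NCS to CS. Show the two shifts to CS first. In the same sentence, name OLE baseline as the reference and state whether the overall or the investigator interpretation governs.

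Optionally, add a 3-by-3 table of OLE baseline against worst post-baseline interpretation, in the form that SAP 9.3.3 uses for laboratory tests.

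The cost is a sentence in the SAP and a changed selection condition on data already collected, plus one table if the option is taken. The downside is a somewhat longer listing. The change will not pick out further worsening in a subject who is already CS at baseline. For those subjects the general listing, the QTcF listings and AE reporting remain the route.

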9.7. Physical Examination

Physical examination findings based on body systems entered on the eCRF will be included in a data listing only.

9.8. Immunogenicity

Immunogenicity of NEOD001 will be assessed by anti-NEOD001 antibody levels. Any sample found to be confirmed positive for anti-NEOD001 antibodies will be further evaluated by a neutralizing antibody assay. Serum anti-NEOD001 antibody levels will be listed.

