5. Record all prior therapies for AL amyloidosis taken prior to signing ICF for this study and since last visit in Study NEOD001-001. Record all prior/concomitant medications taken or received by a subject within the 28 days prior to the Month 1-Day 1 Visit through the EOS Visit, and any changes to concomitant medications during the study. See Study Manual for more information.
6. Adverse events will be collected from the time that the informed consent form is signed through 30 days after the last dose of study drug or last study visit, whichever is later. Record any adverse events that were ongoing from the subject's last visit in Study NEOD001-001 and at the time of the NEOD001-OLE001 Screening Visit.
7. Physical examination will include weight, height (Screening only), and examination of the following: general appearance; head, ears, eyes, nose, and throat; neck; skin; cardiovascular system; respiratory system; abdominal system; and nervous system. A complete physical examination will be done at Screening and EOS; at all other visits, the components of the physical examination will be as clinically indicated. However, at all time points the following should be assessed: macroglossia, submandibular nodes/fullness, adenopathy, ecchymoses, liver/spleen size (palpable +/-), ascites (+/-), and edema (which should be quantified on a scale of 0-4).
8. Vital signs include heart rate (HR), blood pressure (BP), respiratory rate (RR), and body temperature; assess per Section 6.3.2. **Month 1-Day 1:** Predose, halfway through infusion, immediately at EOI (+5 minutes), and 30 (± 5) minutes and 60 (± 10) minutes after EOI. **All Other Months-Day 1:** Predose, EOI (+5 minutes), and 60 (± 10) minutes after EOI.
9. Peripheral neuropathy assessment: only for subjects previously enrolled in Cohort C of Study NEOD001-001.
10. Perform every 3 months (Months 3, 6, 9, 12, etc.).
11. Administer SF-36 before performing any other study assessments on the day it is administered (Appendix 2).
12. Perform every 6 months (Months 6, 12, 18, etc.).
13. NT-proBNP must be drawn before conducting 6MWT, if performed on the same calendar day. Collect blood pressure and heart rate pre- and post-6MWT administration.
14. Two pretreatment 6MWTs are required before the first administration of study drug, with a minimum of 4 days in between the two tests. The second test must be completed 1 to 2 days before the Month 1-Day 1 Visit.

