15. Echocardiogram to be conducted every 12 months and may be conducted within 10 days before the visit.
16. Repeat echocardiogram at EOS if not performed within 60 days prior to visit.
17. For all post-Screening visits, ECGs are to be performed predose and within 15 minutes after the EOI.
18. Conduct telephone call approximately 3 months after subject's last study visit and approximately every 3 months thereafter for up to 5 years, death, or subject withdraws consent, whichever occurs first.
19. Hematology and chemistry per Appendix 3. At Screening, include Screen for Infectious Diseases per Appendix 3. Within 3 days before the first day of a new regimen of chemotherapy, conduct an unscheduled central laboratory collection (including hematology, chemistry, PT/INR, and PTT).
20. Coagulation per Appendix 3. Collect unscheduled citrated plasma samples for subjects with relevant serious adverse event(s); if defects are identified, additional analytes will be analyzed, as indicated (see Appendix 4).
21. All laboratory tests to be done centrally, unless otherwise noted.
22. Perform pregnancy tests for WOCBP as follows: **Screening:** serum test (central) within 28 days before Month 1-Day 1; **Monthly starting with Month 2:** urine test (local) predose; **EOS:** serum test (central). A positive urine pregnancy test (local laboratory) is to be confirmed with a serum pregnancy test (central laboratory).
23. Perform serum pregnancy test (local; WOCBP only) 90 (± 5) days after the last study drug administration.
24. Begin urine collections 24 hours prior to the study visit.
25. After Baseline, use to confirm initial within-study hematologic complete response only.
26. Urinalysis per Appendix 3.
27. NEOD001 serum samples (for population PK analysis): collect predose, at EOI (record the time, but the sample can be collected at any time after the infusion on Day 1), and at other times as clinically indicated, such as when significant toxicity occurs.
28. Anti-NEOD001 antibody samples: collect predose and at other times as clinically indicated, such as when significant toxicity occurs.

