29. NEOD001 will be administered every 28 (± 5) days. Subjects should be closely monitored for 90 (± 10) minutes following completion of the study drug infusion. Beginning with the third infusion, the Investigator may decrease the postdose monitoring time to no less than 60 minutes, if no infusion-related reactions were observed in the previous infusions and allowed per the IRB/IEC. The Investigator may increase the monitoring time if deemed appropriate or per local standards. In the event of any clinical concerns or suspicious signs or symptoms after the infusion, the subject will remain under observation for as long as the Investigator deems it appropriate. If parenteral chemotherapy is administered on the same day as NEOD001, the chemotherapy must be administered **after** the observation period.

Figure 1 NEOD001-OLE001 Study Design

EOS = end of study; ICF = informed consent form.

¹ Maximum dose not to exceed 2500 mg.

² ±5-day window applicable to Months 2+.

GLOSSARY OF TERMS

Abbreviation/Acronym	Definition
AA	Amyloid A
ADA(s)	Anti-drug antibody(ies)
AE	Adverse event
AEF	Amyloid-enhancing factor
AL	Amyloid light chain
ALP	Alkaline phosphatase
ALT	Alanine aminotransferase
ANC	Absolute neutrophil count
ASCT	Autologous stem cell transplant
AST	Aspartate aminotransferase
BP	Blood pressure
BSA	Bovine serum albumin
BUN	Blood urea nitrogen
CTCAE	Common Terminology Criteria for Adverse Events
(E)	Eligibility (i.e., a test that may be used to determine eligibility)
ECG	Electrocardiogram
ECOG	Eastern Cooperative Oncology Group
eCRF	Electronic case report form
EDC	Electronic data capture
EOI	End of infusion
EOS	End of Study
FDA	Food and Drug Administration
GCP	Good Clinical Practice
GGT	Gamma-glutamyl transpeptidase
HIV	Human immunodeficiency virus
HR	Heart rate

Abbreviation/Acronym	Definition
ICF	Informed consent form
ICH	International Council for Harmonisation
IEC	Institutional Ethics Committee
IFE	Immunofixation electrophoresis
IgG1	Immunoglobulin G1
INR	International normalized ratio
IRB	Institutional Review Board
IV	Intravenous(ly)
LDH	Lactate dehydrogenase
NT-proBNP	N-terminal pro B-type natriuretic peptide
NYHA	New York Heart Association
PCD	Plasma cell dyscrasia
PEP	Protein electrophoresis
PK	Pharmacokinetic(s)
PS	Performance status
PT	Prothrombin time
PTT	Partial thromboplastin time
QTc	Corrected QT interval
RBC	Red blood cell
RR	Respiratory rate
SAE	Serious adverse event
SFLC	Serum free light chain
SIFE	Serum immunofixation electrophoresis

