6.4 PHARMACOKINETIC AND IMMUNOGENICITY ASSESSMENTS

All subjects enrolled in the study will undergo sparse sampling for serum NEOD001 according to [Table 1](#). Serum NEOD001 concentrations from this study will be pooled with similar samples from other studies in a population PK analysis. Details will be provided in a separate document.

Serum anti-NEOD001 antibody levels will be measured according to [Table 1](#). An electrochemiluminescent assay will be used to detect serum anti-NEOD001 antibodies. Any screening positives will be run at increasing dilutions to and a titer determined (expressed as the reciprocal of the dilution that generates a positive response). Additionally, all positives will be run in a confirmatory assay to determine the response is specific to NEOD001.

Additional samples for anti-NEOD001 antibodies and serum NEOD001 should be collected if a significant toxicity is observed (e.g., an infusion reaction in the clinic, anaphylaxis, etc.) and if possible, should be collected while the acute symptoms persist.

Refer to the Laboratory Manual for additional details.

7 **ADVERSE EVENTS/SERIOUS ADVERSE EVENTS AND REPORTING**

7.1 **ADVERSE EVENTS—DEFINITION**

An AE is any untoward medical occurrence associated with the use of a drug in humans, whether or not considered drug related. An AE can therefore be any unfavorable and unintended sign (including a laboratory finding, for example), symptom, syndrome, or disease temporally associated with the use of a medicinal product, whether or not considered related to the medicinal product. Examples include:

- Any treatment-emergent signs and symptoms (events that are marked by a change from the subject's baseline/entry status [e.g., an increase in severity or frequency of preexisting abnormality or disorder])
- All reactions from study drug, abuse of drug, withdrawal phenomena, sensitivity, or toxicity to study drug
- Apparently unrelated illnesses
- Injury or accidents
- Exacerbations of the underlying disease (indication)
- Extensions or exacerbations or symptomatology, subjective events reported by the subject, new clinically significant abnormalities in clinical laboratory, physiological testing, or physical examination

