8.5.2 Immunogenicity

Serum anti-NEOD001 antibody titers will be listed and correlated with clinical toxicity. Anti-NEOD001 antibody levels will be correlated with NEOD001 exposure level to assess potential dose concentration related associations when anti-NEOD001 antibody and corresponding PK data are available.

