4.6. Analysis Visit Windows

Each visit will be denoted by its “month” and “day” such that the first dose day is denoted as Month 1-Day 1; subsequent months will use sequential numbers (e.g., the second dose is administered on Month 2-Day 1). Each infusion is scheduled to be 28 days from the previous infusion (± 2 days for Months 2 and 3; ± 5 days for Months 4 and beyond).

“Cycle” is reserved to denote administration of chemotherapy. It is expected that all visits should occur according to the protocol schedule.

In data listings, the relative study day from first infusion of all dates will be presented.

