4.6.1. NEOD001 Therapy Visit Windows

Table 2 defines the visit windows for assessments taken at 1-month intervals to be established with respect to relative day from the start of NEOD001 therapy.

Table 2: NEOD001 Therapy 1-Month Interval Visit Windows (Days)

Months	Target Study Day ^a	Analysis Window Study Day ^a	
		Low	High
NEOD001 Baseline ^b	1	Closest visit to Day 1, prior to first NEOD001 dose	
NEOD001 Month 1	28	2	42 [= 28 + 28/2]
NEOD001 Month 2	56	43 [= (28 + 28/2 + 1)]	70 [= 56 + 28/2]
NEOD001 Month x	28*x	(x-1)*28 + 28/2 + 1	x*28 + 28/2

^a Study day will be calculated from first dose date according to Section 2.2.4.1.

^b NEOD001 Baseline is defined in Section 2.2.4.1.

Table 3 defines the visit windows for assessments taken at 3-month intervals to be established with respect to relative day from the start of NEOD001 therapy.

Table 3: NEOD001 Therapy 3-Month Interval Visit Windows (Days)

Months	Target Study Day ^a	Analysis Window Study Day ^a	
		Low	High
NEOD001 Baseline ^b	1	Closest visit to Day 1, prior to first NEOD001 dose	
NEOD001 Month 3	84	2	126 [= 84 + 84/2]
NEOD001 Month 6	168	127 [= (84 + 84/2) + 1]	210 [= (168 + 84/2)]
NEOD001 Month x	28*x	(x-3)*28 + 84/2 + 1	x*28 + 84/2

^a Study day will be calculated from first dose date according to Section 2.2.4.1.

^b NEOD001 Baseline is defined in Section 2.2.4.1.

The duration of 60 days between the time from last dose in the original parent study (NEOD001-001) to first dose in the OLE was chosen based on PK experience of elimination of study drug.

Note that the assessment used in the analyses is chosen step by step as follows in cases when multiple records exist within the same analysis window:

1. Choose the assessments with shortest distance from the target day.
2. If multiple assessments are the same distance from the target day for a particular analysis window, the later assessments are chosen.
3. If there are 2 or more assessments taken on the same date or same date and time, the rules for choosing the assessment are:
 - a. First take the assessment from the scheduled visit, then take the assessment from the re-test visit (applicable to laboratory tests), then take the assessment from the discontinuation visit, then take the assessment from the unscheduled visit.
 - b. Take the assessment with the most abnormal value.
 - Most abnormal value is determined by taking the value that is the further from the lower limit of normal (LLN) or ULN.

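### Antibody samples are drawn while NEOD001 is probably still in serum, and neither document says how to read a negative result when drug is present

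*SAP*

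**What the plan says.** Immunogenicity is the first secondary objective in both documents. SAP 9.8 sets the measure: "Immunogenicity of NEOD001 will be assessed by anti-NEOD001 antibody levels".

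- **Sampling.** Protocol Table 1 schedules antibody samples at Screening, every 3 months on treatment and at EOS. Footnote 28 reads: "Anti-NEOD001 antibody samples: collect predose and at other times as clinically indicated, such as when significant toxicity occurs". Footnote 29 sets the dosing interval: "NEOD001 will be administered every 28 (± 5) days". EOS is 30 (±5) days after the last dose.
- **Assay.** Protocol 6.4: "An electrochemiluminescent assay will be used to detect serum anti-NEOD001 antibodies". Samples that screen positive are titrated and go to a confirmatory assay. SAP 9.8 adds a neutralizing assay for confirmed positives. No step applies to a negative. Further assay detail is left to the Laboratory Manual.
- **Elimination.** SAP 4.6.1 says the 60-day interval from the last parent-study dose "to first dose in the OLE was chosen based on PK experience of elimination of study drug". SAP 2.2.4.1 uses that interval to choose which baseline applies.
- **Reporting.** Protocol 8.3 summarizes antibody incidence. Protocol 8.5.2 says "Anti-NEOD001 antibody levels will be correlated with NEOD001 exposure level to assess potential dose concentration related associations", where both results exist. SAP 9.8 only lists antibody levels, and SAP 2.3.2.1 makes the correlation optional. SAP 11 records the loss of efficacy summaries but no change to immunogenicity reporting.
- **Paired drug level.** Table 1 schedules a serum NEOD001 sample at the same visits (Screening, predose every 3 months, EOS). SAP 10 lists those concentrations separately.

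**The concern.** Drug in a serum sample can bind anti-drug antibody and keep it from being detected. If the concentration exceeds what the assay tolerates, a negative does not show that antibody is absent. The plan follows up positives in three ways (titre, confirmation, neutralization) and says nothing about negatives, so a masked sample would by default be listed and counted as negative.

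Two planned outputs are exposed. Antibody incidence would be pulled towards zero. The antibody-exposure correlation could show an inverse association from interference alone, and that would look the same as antibody speeding up clearance. Protocol 1.3.2 already reports no confirmed antibodies in the parent study, so a second zero could be taken as corroboration.

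**Working it through.** The documents give no half-life, drug tolerance or detection rate, so there is no planned figure to reproduce. Step 1 uses the documents only. Steps 2 to 4 are illustrations under stated assumptions.

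**1. Timing of samples.**
- On treatment: Months 3, 6, …, 36 give 36/3 = 12 samples per subject, plus one at EOS.
- Predose: 28 − 5 = 23 to 28 + 5 = 33 days after the previous infusion. Protocol 6.1.2 asks for predose assessments 1 to 2 days before Day 1, so the earliest is about 23 − 2 = 21 days.
- EOS: 30 − 5 = 25 to 30 + 5 = 35 days.
- Overall: about 21 to 35 days, against 60 days.
- SAP 4.6 agrees on the nominal interval ("Each infusion is scheduled to be 28 days from the previous infusion") but gives ±2 days for Months 2 and 3 where the protocol gives ±5. The two must be reconciled; the difference does not change this result.
- The only later planned sample is in Protocol 4.3, three months after EOS: 25 + 91 = 116 to 35 + 91 = 126 days after the last dose. It applies only after discontinuation for a suspected immunologic reaction, and only if the subject agrees.

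**2. Share of a single dose remaining.** Assume one-phase elimination and that 60 days is 3 to 5 half-lives, so t½ = 60/3 = 20 to 60/5 = 12 days. Share = 2^(−t/t½).

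| Day | t½ 12 d | t½ 20 d |
|---|---|---|
| 28 | 19.8% | 37.9% |
| 30 | 17.7% | 35.4% |
| 60 | 3.1% | 12.5% |

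**3. Concentration at steady state.** Assume 70 kg, one compartment and V = 3 or 5 L. Dose = 24 × 70 = 1680 mg. C0 = 1680/V = 560 or 336 µg/mL. Predose = C0·f/(1 − f) with f = 0.5^(28/t½). EOS = C0·0.5^(30/t½)/(1 − f).

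Example, V = 3 and t½ = 12: f = 0.198, and 560 × 0.198/0.802 = 138.6 µg/mL with unrounded f.

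| t½ (d) | Predose, V=3 | Predose, V=5 | EOS, V=3 | EOS, V=5 |
|---|---|---|---|---|
| 7 | 37.3 | 22.4 | 30.6 | 18.4 |
| 12 | 138.6 | 83.2 | 123.5 | 74.1 |
| 15 | 211.6 | 126.9 | 192.9 | 115.7 |
| 20 | 341.7 | 205.0 | 318.8 | 191.3 |

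The range is 18.4 to 341.7 µg/mL. Even at 7 days, where 60 days is 60/7 = 8.6 half-lives, drug remains.

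**4. What a zero would mean.** For a hypothetical 0 positives in 70 subjects, the one-sided 95% upper bound is 1 − 0.05^(1/70) = 4.2%. If an antibody-positive subject is detected with probability s, the bound becomes 4.19%/s: 8.4% at s = 0.5 and 16.8% at s = 0.25. Both values of s are assumed. With up to 13 samples per subject, s is low only if masking persists across visits.

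**The case against.** The strongest reply is that the deciding figure is absent. Interference matters only if drug exceeds the assay's tolerance, and that limit, perhaps with a reporting rule, may be in the Laboratory Manual. A range of 18 to 342 µg/mL cannot be compared with an unknown limit. This stands: interference is possible, not shown. It does not supply the missing analysis rule, because the SAP neither states nor refers to a tolerance.

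Other points on that side:

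- **The 60 days is a baseline-selection rule.** Correct. A reader might take it as an assay washout limit, which it is not. Its stated basis is elimination, so it supports residual drug being likely at 3 to 5 weeks and nothing more precise.
- **Not every sample fits.** Withheld doses lengthen the gap. The 2500 mg cap and 50% reductions lower the concentration. Screening samples can be drug-free after a long gap since parent dosing. These are exceptions to the routine schedule.
- **The SAP only lists levels and makes the correlation optional.** Correct, but Protocol 8.3 and 8.5.2 still plan incidence and correlation, and SAP 11 does not withdraw them.
- **The paired concentrations are already listed.** Correct, and this is why the remedy is cheap. Without a tolerance, though, a reader with two listings cannot tell which negatives are interpretable.
- **A sample 3 months after EOS exists.** It covers a suspected reaction and not routine negatives.

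**Conclusion.** The point holds in a limited form. With dosing on schedule, on-treatment and EOS antibody samples fall about 21 to 35 days after an infusion, inside the SAP's elimination-based 60 days. Drug is probably present, and neither document says how to treat a negative in that setting. Bias of incidence towards zero and distortion of the exposure correlation are real possibilities for a secondary objective.

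Their size is unknown. The concentrations rest on assumed weight, volume, half-life and one-compartment kinetics, and the 8.4% and 16.8% bounds rest on assumed detection probabilities.

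A reader might infer that the negatives are false, that the immunogenicity result will be falsely reassuring, or that the parent study's zero is an artefact. The documents support none of these, because they contain no drug tolerance and no measured trough. This is an inexpensive improvement to the plan and not a demonstrated error in its results.

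**What to change.** In SAP 9.8 and 2.3.2.1:

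1. State the assay's validated drug tolerance.
2. List each antibody result beside the paired NEOD001 concentration (predose, EOS or Screening) from Table 1.
3. Label a negative *inconclusive* when that concentration exceeds the tolerance.
4. Report antibody incidence with the numbers of evaluable and inconclusive samples, and reconcile the SAP's listing-only wording with Protocol 8.3.
5. Limit any antibody-exposure correlation to evaluable samples.

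The cost is SAP wording and one merge of two existing datasets; no new samples are needed. If the assay tolerates the concentrations found, no result changes and the negatives become easier to defend. If tolerance is low, many on-treatment and EOS negatives become inconclusive and few evaluable samples may remain.
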